¹³Blood pressure and heart rate are also assessed at the start of every session for patients in the SE (intervention) arm who are known to have high blood pressure, history of unstable blood pressure, symptomatic, or reports new treatment. If 2/3 readings demonstrate the pressure to be >160 OR >90 at the time of the session, exercise will be held on that day.

¹⁴Continuously reported from informed consent until 28 days after Cycle 24, Day 1. All adverse events (AE) should be followed to their resolution, until the PIs assess them as stable, irreversible, or until the patient refuses further follow up, whichever comes first. AEs are assessed by the exercise physiologist, trainer, etc. at on-site exercise visits and in all subjects (in person or by phone) on a monthly basis. AE events will be recorded on the AE form and logged in REDCap. AE assessment will include bone pain.

¹⁵Medications will be reviewed with the patient once a month, either in person or by phone call. Medications will be logged and entered into the REDCap database.

¹⁶Sec 8.3: Baseline blood collection will occur after the patient passes the baseline CPET, and will occur before or on Day 1, Cycle 0, before the remainder of the exercise tests are performed and at least 48 hours after any vigorous activity including the screening CPET visit

¹⁷Sec 8.3: Follow-up blood collection will occur prior to completing the exercise tests on that day (see footnote #11), and at least 48 hours after any vigorous activity. If it cannot be completed on that day, it must be completed within 7 days after Day 1 of the Cycle, at least 48 hours after any vigorous activity.

¹⁸Request access to available archival formalin-fixed paraffin-embedded (FFPE) tumour blocks or tumour slides from consenting patients for future biomarker analyses.

¹⁹The baseline surveys or FFQ will be completed within 28 days prior to the screening CPET and used as the baseline assessments

²⁰[Appendix 6, 20-27, 29, 31, 33](#). All follow-up surveys and FFQ will be completed within 7 days before the exercise assessment, except for [Appendix 20, 24, and 33](#), which are completed on paper at the visit or by mail.

²¹Selected assessments will be administered during the follow-up period on a yearly basis. If no response is received from the participant and medical records do not indicate death, we will follow up with the next of kin or alternate contact.

⁸New conditions diagnosed on-study are recorded during the on-study period.

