5.5.4.1 Record date of assessment

5.5.4.2 Confirm completion of questionnaires

5.5.4.3 Record any adverse events and changes to concomitant medications. Record bone pain (VAS) and fatigue (VAS).

5.5.4.4 Record resting measures including resting blood pressure, resting heart rate and SpO₂, ECOG

5.5.4.5 Perform cardiopulmonary exercise test with ECG (Day 1 of cycle 6 and 12 only)

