- 5.5.6 Every 7 Days for 8 cycles starting from Cycle 1 (within 7 days on or after Day 1) – One to two Exercise Training Visits and One Self-Managed Exercise Session per 7 Days for ARM A**

Exercise session (2 supervised sessions and 1 self-managed session per 7 days)

- **Day 1 (Supervised)**
 - **Assessment:** Bone pain (VAS), Fatigue (VAS), resting heart rate, resting blood pressure and record any new adverse events or changes to medication.
 - **Warm up:** 5 minutes cycling at a light to moderate intensity
 - **Exercise:** High load, low volume resistance training; high-intensity interval aerobic training.
 - **Outcomes:**
 - Resistance Exercise: Number of sets, number of repetitions, weight lifted.
 - Aerobic Exercise: Work interval, rest interval, number of repetitions, RPE achieved.
 - Sessional Data: Sessional RPE, post-aerobic heart rate, post-session blood pressure
 - **Cool down:** Trunk flexion and extension exercises and static stretching
- **Day 2 (Self-Managed)**
 - **Assessment:** Bone pain (VAS), Fatigue (VAS), resting heart rate, resting blood pressure and record any new adverse events or changes to medication.
 - **Warm up:** 5 minutes cycling at a light to moderate intensity
 - **Exercise:** High intensity continuous aerobic training.
 - **Outcomes:**
 - Aerobic Exercise: Work interval, rest interval, number of repetitions, RPE achieved.
 - Sessional Data: Sessional RPE, post-aerobic heart rate, post-session blood pressure
 - **Cool down:** Trunk flexion and extension exercises and static stretching
- **Day 3 (Supervised)**
 - **Assessment:** Bone pain (VAS), Fatigue (VAS), resting heart rate, resting blood pressure and record any new adverse events or changes to medication.
 - **Warm up:** 5 minutes cycling at a light to moderate intensity
 - **Exercise:** Moderate load and volume resistance training; high-intensity interval aerobic training

- **Outcomes:**
 - Resistance Exercise: Number of sets, number of repetitions, weight lifted.
 - Aerobic Exercise: Work interval, rest interval, number of repetitions, RPE achieved.
 - Sessional Data: Sessional RPE, post-aerobic heart rate, post-session blood pressure
- Cool down:** Trunk flexion and extension exercises and static stretching

5.5.7 Every 7 Days for 3 cycles starting from Cycle 9 (within 7 days on or after Day 1) – One Exercise Training Visit and Two Self-Managed Exercise Sessions per 7 Days for ARM A

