Exercise session (one supervised session and two self-managed sessions per 7 days):

- **Day 1 (Supervised)**
 - **Assessment:** Bone pain (VAS), Fatigue (VAS), resting heart rate, resting blood pressure and record any new adverse events or changes to medication.
 - **Warm up:** 5-10 minutes cycling at a light to moderate intensity
 - **Exercise:** High load, low volume resistance training; high-intensity interval aerobic training.
 - **Outcomes:**
 - Resistance Exercise: Number of sets, number of repetitions, weight lifted.
 - Aerobic Exercise: Work interval, rest interval, number of repetitions, RPE achieved.
 - Sessional Data: Sessional RPE, post-aerobic heart rate, post-session blood pressure

Cool down: Trunk flexion and extension exercises and static stretching
- **Day 2 (Self-Managed)**
 - **Assessment:** Bone pain (VAS), Fatigue (VAS), resting heart rate, resting blood pressure and record any new adverse events or changes to medication.
 - **Warm up:** 5 minutes cycling at a light to moderate intensity
 - **Exercise:** High intensity continuous aerobic training.
 - **Outcomes:**
 - Aerobic Exercise: Work interval, rest interval, number of repetitions, RPE achieved.
 - Sessional Data: Sessional RPE, post-aerobic heart rate, post-session blood pressure

Cool down: Trunk flexion and extension exercises and static stretching
- **Day 3 (Self-Managed)**
 - **Assessment:** Bone pain (VAS), Fatigue (VAS), resting heart rate, resting blood pressure and record any new adverse events or changes to medication.
 - **Warm up:** 5 minutes cycling at a light to moderate intensity
 - **Exercise:** High load, low volume resistance training; high-intensity interval aerobic training.
 - **Outcomes:**
 - Resistance Exercise: Number of sets, number of repetitions, weight lifted.
 - Aerobic Exercise: Work interval, rest interval, number of repetitions, RPE achieved.
 - Sessional Data: Sessional RPE, post-aerobic heart rate, post-session blood pressure

Cool down: Trunk flexion and extension exercises and static stretching

5.5.8 Day 1 of Cycles 0-23 (within 7 days on or after Day 1) – Exercise Testing in ARM A

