5.5.8.1 Record date of assessment

5.5.8.2 Perform constant load exercise test

5.5.8.3 Complete 1RM testing; chest press, leg press, seated row, and leg extension (Cycles 0, 6, 9, 12 and 18)

5.5.9 Every 6 cycles (Cycle 6, 12, 18, and 24) within 7 days of Day 1

Medical clearance(s)* must be obtained from the patient's treating physician **prior** to exercise testing and/or training on Day 1 in the absence of any SAEs (SOM: [Appendix 9](#)).

* For any patient under that management of a cardiologist, additional clearance by his cardiologist is necessary at Cycles 0, 6, and 12.

5.5.10 Cycle 24/ Off-Study visit (within 7 days on or after Day 1) ARMS A & B

- Collect updated medical history
- Record ECOG PS, vital signs, patient weight, waist, and hip circumference
- Note concomitant medications (including WHO analgesic scale) and adverse events
- Assess disease progression from baseline
- Record any symptomatic-skeletal events
- 1-RM testing
- 400 m walk test
- Constant Load Exercise Test (Arm A only)
- Collect Research Blood and Urine
- BPI-SF, FACT-G, EPIC-26, FACIT-Fatigue, EQ5D, EORTC QLQ-30, STAI, CES-D (if not completed within 42 days – half the time between questionnaire assessments)
- Modified Godin, other exercise, and memory questionnaire (if not completed within 84 days - half the time between questionnaire assessments)
- FFQ (doesn't follow the 84-day stipulation)

5.5.11 Safety Follow-up (28 Days following Day 1 Cycle 24) ARMS A & B

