2x week self-managed; 1x week supervised Cycles 9-11	The behavioural support will focus on: 
 ○ Identifying and overcoming barriers to exercise ○ Finding areas/ways/places to exercise ○ Self-monitoring ○ Goal setting ○ Time management ○ Lapsing/Relapsing/Collapsing ○ Gaining confidence ○ Perceived independence ○ Making exercise fun ○ Perceived competence ○ Staying motivated ○ Maintaining/enhancing self-efficacy ○ Securing social support 
 ➤ 3x per week pt. would get a text message emphasising 2 of the topics above “signed” by the exercise specialist – each week would be a different pair working “down” off the list
Totally self-managed; 1x supervised session approximately every four weeks Cycles ≥ 12	The behavioural support will focus on a ‘kitchen sink’ approach: 
 ○ Identifying and overcoming barriers to exercise ○ Finding areas/ways/places to exercise ○ Self-monitoring ○ Goal setting ○ Time management ○ Lapsing/Relapsing/Collapsing ○ Gaining confidence ○ Perceived independence ○ Making exercise fun ○ Perceived competence

- Staying motivated
- Maintaining/enhancing self-efficacy
- Securing social support
- 5x per week pt. would get a text message emphasising 2 of the topics above “signed” by the exercise specialist – each week would be a different pair working “down” off the list.

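### Footnote 13 limits start-of-session blood pressure to a subset, so from Cycle 12 other exercise-arm men have 10 cycles of supervised exercise with no listed prior reading

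*Combined protocol and SAP*

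**What the plan says.** Footnote 13 to Table 1 sets who has blood pressure and heart rate taken at the start of every session: "patients in the SE (intervention) arm who are known to have high blood pressure, history of unstable blood pressure, symptomatic, or reports new treatment". It then gives the hold rule: "If 2/3 readings demonstrate the pressure to be >160 OR >90 at the time of the session, exercise will be held on that day".

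The session descriptions for Cycles 0-11 (Sections 5.5.5 to 5.5.7) carry no such restriction. For every Arm A man, at supervised and self-managed sessions alike, the assessment includes "resting heart rate, resting blood pressure and record any new adverse events or changes to medication".

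From Cycle 12, readings for all men are listed at the six-cycle assessments and at the end of the intervention. Section 5.5.4.4, for Cycles 6, 12, 18 and 24, says "Record resting measures including resting blood pressure, resting heart rate". Section 5.5.10, for the Cycle 24 or Off-Study visit, says "Record ECOG PS, vital signs, patient weight, waist, and hip circumference".

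Supervised exercise does not stop at Cycle 12. Table 4 gives "1x supervised session approximately every four weeks" for Cycles 12 and later. Section 5.5.8, which covers Arm A testing in Cycles 0-23, has the step "Perform constant load exercise test" and lists no blood pressure step.

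**The concern.** The hold rule is the protocol's direct safeguard against exercising a man whose pressure is too high that day, and it works only where a reading is taken. In Year 1 the session descriptions provide one every time. In Year 2 only footnote 13 calls for session readings, and it covers a subset defined by what is already known or reported. A rise in pressure that causes no symptoms is what that subset cannot pick up.

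The exertion is not trivial. Section 5.2.4 sets the constant load test at 70% of the maximal workload from the first cardiopulmonary exercise test (CPET), so the load stays fixed while the man's condition may change.

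The two rules also disagree within Year 1. A site that followed footnote 13 alone could omit readings that 5.5.5 to 5.5.7 list for everyone. What is at stake is participant safety and a consistent instruction to sites.

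**Working it through.** This is a count from the schedule; no sample-size or power figure enters.

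**1. Check that the schedule is read correctly.** Supervised sessions in Cycles 0-11: 3 × 4 + 2 × 32 + 1 × 12 = 88, which reproduces the 88 in Section 6.1. Self-managed sessions: 0 × 4 + 1 × 32 + 2 × 12 = 56. Total: 88 + 56 = 144 planned sessions, each with a listed resting blood pressure under 5.5.5 to 5.5.7.

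**2. Cycles from 12 on without a listed reading, for a man outside the subset.**
- Cycles 12-23 with supervised exercise: 12. Readings for all men fall in Cycles 12 and 18. 12 − 2 = 10.
- Counting Cycle 24 as well: 13 − 3 = 10.
- The cycles are 13-17 (5) and 19-23 (5).

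Cycles 12 and 18 are treated as fully covered, although the supervised session there may fall on a different day from the assessment.

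**3. Interval between listed readings.** 6 cycles × 28 days = 168 days.

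**4. Could another section supply the reading?**
- Section 5.2.4 names what the constant load test measures: perceived exertion and three heart-rate measures. Blood pressure is not among them. Section 5.2.1 does name it for the CPET.
- The sections disagree on whether the last CPET is at Cycle 12 (5.2, 5.5.4.5) or Cycle 18 (5.2.1). Both cycles already count as covered, so the 10 is unchanged.
- Sections 6.1.2 and 6.1.4 mention the constant load test only for Cycles 0-11, whereas Table 1, 5.2 and 5.5.8 continue it. If it did stop, the monthly supervised session would leave the same 10 cycles.
- Medical clearance is due every six cycles, and Section 5.1.3 leaves any physical exam to the doctor.
- Medications are reviewed monthly, in person or by phone (footnote 15).

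**5. Effect of adding a reading before each supervised session and test.** Cycles without a listed reading fall from 10 to 0, and the interval falls from 168 to about 28 days.

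**The case against.** The strongest reply is that the protocol is silent here rather than deciding against a reading. No part of Section 5.5 describes a supervised training session after Cycle 11 at all, and the protocol sends the detail of assessments and training to the SOM. That stands as a caution. A reader might infer that men train in Year 2 with no blood pressure monitoring; the documents do not show that, because the SOM may require a reading. It does not remove the point, because footnote 13 is itself a stated rule and is narrower than 5.5.5 to 5.5.7.

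Other safeguards are real. Under footnote 14, adverse events are assessed in person at on-site exercise visits, and a man who reports symptoms enters the subset. Table 5 applies to testing and training and lists stops for a fall in systolic pressure. One of these is a fall below standing resting pressure, which presupposes a resting value. But Table 5 schedules no resting reading, and its entry for a hypertensive response has no threshold. These checks narrow the gap without closing it.

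It is also fair to say that risk-based checks are a defensible choice in men who passed the screening limit of 160/90 and had a year of listed session readings. A man found high in that year can be read as known to have high pressure, and so stays covered. This is why the remaining risk is small.

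A reader of footnote 13 alone might extend the gap to the whole intervention: 24 cycles (0-23) less the four with vital signs (0, 6, 12, 18) gives 20. Sections 5.5.5 to 5.5.7 rule that out for Cycles 0-11.

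**Conclusion.** The point holds as a cheap safety improvement. On the visible text, an exercise-arm man outside the footnote 13 subset who stays on the intervention has 10 cycles (13-17, 19-23) in which a supervised session and a constant load test take place with no listed prior reading, and the hold cannot act. The risk left over is a symptom-free rise in a man with no new treatment and no high reading in Year 1.

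The count of 10 rests on the schedule alone. Confidence in the practical consequence is moderate, because the SOM was not available.

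Two larger conclusions are not supported. A reader might scale the gap up to a trial-wide number of patient-cycles. The documents do not give the share of men outside the subset, and that share falls over time as men start new treatment and so join it; any total built on a constant assumed share would be an upper-end illustration at best. A reader might also look for an effect on overall survival or its analysis; nothing in the documents supports one.

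**What to change.** **Footnote 13.** Require blood pressure and heart rate at the start of every supervised session and before every constant load test for all exercise-arm patients, and state that the hold applies to all of them. Keep the readings at self-managed sessions listed in 5.5.6 and 5.5.7, and keep the subset's readings at every session, including self-managed ones after Cycle 12.

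**Section 5.5.8.** Before 5.5.8.2, add a step to record resting blood pressure and heart rate and apply the footnote 13 hold. Sections 5.5.5 to 5.5.7 need no change.

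If the SOM already requires these readings, align the protocol wording with it.

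**Cost.** Wording in two places, and about 10 checks per man outside the subset over Cycles 12-23 if the test and the session share a visit. If they fall on separate days, up to 10 tests + 12 sessions = 22 checks. At 10 checks, that is 10 readings if one suffices each time, or 20 to 30 if two or three are always taken. An occasional session will be held. No new equipment is needed, since 5.5.4.4 already asks for this reading.

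**Limit.** The change does not reach self-managed sessions after Cycle 12 in men outside the subset, and these make up most of the exercise in that period. At two resistance sessions a week (Section 6.1.4), resistance work alone comes to 2 × 48 = 96 sessions over Cycles 12-23.

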5.1 Clinical Assessments

5.1.1 Demographic Information

Demographic information (e.g., date of birth, race, marital status, education) will be recorded at Screening via questionnaire.

5.1.2 Clinical History

Relevant medical history, including current disease, other pertinent clinical conditions, and information regarding underlying diseases will be recorded at Screening (see Medical History section in [Appendix 5](#)).

The following items should be reported:

- **Medical History:** includes history of other disease processes (active or resolved) not related to the diagnosis of prostate cancer, concomitant illnesses
- **Prostate Cancer History:** histology of the tumour, date of the histological diagnosis, clinical Tumour Nodes Metastasis (TNM) stage at diagnosis, Gleason score of the tumour at diagnosis (biopsy and surgical, if available)
- **Tumour histology:** Adenocarcinoma, adenocarcinoma with small cell neuroendocrine features, small cell neuroendocrine. Men with small cell neuroendocrine disease or features are not eligible.
- **Comprehensive treatment history:** Select treatment information for prostate cancer and the start and stop dates.
- **Current sites of metastasis:** Lymph nodes, bone, liver, lung, other, or none.

5.1.3 Physical Exam

We request a medical clearance from their general practitioner (MD) or treating oncologist to confirm the patient is physically and psychologically able to participate in the trial. We leave it up to their doctor to determine if they require a physical exam. Weight, Height, Waist Circumference, Hip Circumference and Vital Signs should be measured as per the schedule of assessments (see [Table 1](#)). Descriptions and instructions pertaining to these assessments are provided in the SOM.

5.1.4 Performance Status

The ECOG performance status scale will be used (SOM: [Appendix 7](#)) and assessed by authorised site personnel (the physician at the time of physician clearance or exercise physiologist/trainer, if regularly-performed task).

5.1.5 Concomitant Medications/Therapies

Standard medical treatment as applicable is allowed. Additionally, any therapy initiated after randomisation for the treatment of MCRPC should be preceded by documented clinical evidence of disease progression, a SSE, pain, or other clinical indication. Every medication or treatment taken by the patient during the trial and the reason for its administration must be recorded on the CRF. All concomitant medication and concurrent therapies will be documented from informed consent until 28 days after Cycle 24 (end of intervention): name, indication for administration, and dates of medication or therapy (SOM: [Appendix 11](#)).

5.1.6 Opiate Use (see WHO analgesic scale in SOM: [Appendix 28](#))

Opiate use will be obtained every 3 cycles through medical record review. The WHO analgesic score will be used to grade opiate use according to the following criteria; 0 = no use; 1 = use of non-opiate analgesics (eg, non-steroidal anti-inflammatory drugs, acetaminophen, antidepressants, and agents targeting neuropathic pain; 2 = use of weak opiates for moderate pain (e.g., codeine and tramadol); 3 = strong opiates for severe pain (e.g., morphine and fentanyl).

5.2 Exercise Laboratory Measurements (SOM: [Appendices 14-16](#))

The following exercise assessments will be completed in both the intervention and the control group at screening/baseline (see note) and within 7 days on or after day 1 of Cycle 6, 12, 18 and 24, subject to location of bone metastases.

NOTE: The first cardiopulmonary exercise test will be completed during the screening period to ensure eligibility. The results of the screening measure will be used as the baseline result. Subsequent assessments will be completed over two days (Day 1: Cardiopulmonary exercise test; Day 2: 400m Walk test, 1RM test) at least 48 hours apart for Cycle 6 and Cycle 12, and over 1 day for Cycles 18 and 24.

1. Cardiopulmonary Exercise Test (During screening 2-14 days prior to Cycle 0, and within 7 days on or after Day 1, Cycle 6 and 12)
2. 400m Walk Test (completed on Cycle 0, and within 7 days on or after Day 1, Cycle 6, 12, 18, and 24)
3. Strength assessment (completed on Cycle 0, and within 7 days on/after Day 1, Cycle 6, 12, 18, and 24)
 - a. 1RM Chest Press
 - b. 1RM Leg Press
 - c. 1RM Seated Row
 - d. 1RM Leg Extension

Aerobic fitness and muscle strength will be monitored in the exercise intervention group only to inform exercise prescription and progression throughout the supervised exercise program. The following exercise monitoring assessments will be completed, subject to location of bone metastases.

1. Strength assessment (completed within 7 days on or after Day 1 of Cycle 9)
 - a. 1RM Chest Press
 - b. 1RM Leg Press
 - c. 1RM Seated Row
 - d. 1RM Leg Extension
2. Constant Load Exercise Test (completed within 7 days on or after Day 1 of Cycle 0-24/Off-Study Visit)

Full details of all assessments can be found in SOM: [Appendix 13: Exercise Physiologist Manual #1 – Exercise Testing Instructions](#).

5.2.1 Cardiopulmonary Exercise Test with Electrocardiogram (ECG)

Maximal oxygen uptake (VO_{2max}) will be measured using a cycle ergometer-based CPET during screening (2-14 days prior to Cycle 0, Day 1) and within 7 days on or after Day 1 of Cycles 6 and 18. Gas exchange will be measured by indirect calorimetry. Participants must receive medical clearance to complete testing. For any participants currently under the management of a cardiologist, their additional clearance is required. Pre-test resting heart rate, blood pressure, respiratory rate and ECG readings must be recorded. A standard 12-lead ECG (with a 10-second rhythm strip) will be collected prior to, during, and for 5-minutes after all CPETs. The pre-exercise ECGs will be collected after the patient has rested quietly and is awake in a fully supine (or semi-recumbent, if supine is not tolerated) position for 10 minutes, and prior to any blood draw collection. Subsequent pre-exercise ECG readings should be collected with the patient in the same position (e.g., fully supine or semi-recumbent).

The exercise test will last approximately 8-12 minutes, commencing at a light cycling load that will progress incrementally during the test. A ramped protocol, starting at 20W (linearly increasing at 10 W/min or 15 W/min) as suited to the participant should be completed. A pedalling frequency of 70-80 RPM should be maintained during the test. The test is terminated when cycling speed falls below 50RPM despite motivation, due to physical fatigue. Participants should achieve volitional exhaustion ($RPE \geq 9$ using the Borg 0-10 RPE scale) after 8 (or more) minutes, in the absence of any cardiorespiratory abnormalities to indicate that maximal load has been

achieved. Objectively, to assist practitioners with delivering valid CPET assessments, patients nearing exhaustion should be achieving a respiratory exchange ratio (RER) near ≥ 1.1 ; however RER is not a required criteria of the test. The test concludes with participants completing 5 minutes cycling at 10W. Blood pressure, heart rate, RPE and ECG will be measured at regular intervals throughout the test and during recovery. If the patient or exercise physiologist accidentally or incorrectly stops the test prior to volitional exhaustion, a repeat test can be provided within the same session after a 10 minute rest, providing the patient, exercise physiologist and supervising medical doctor are satisfied that a second trial is likely to be successful.

5.2.2 400m Walk Test

The 400m walk test is a self-paced, submaximal exercise test. The time taken to complete the 400m course correlates well with VO_2 max and will provide a surrogate measure of aerobic fitness and physical function during the intervention. Participants will be required to move as fast as they can along a 20m course, demarked by two cones, until they have completed 10 laps of the course (400m). The time taken to complete the test will be recorded. Heart rate will be measured pre-test, immediately post-test, 1-minute post-test and 2-minutes post-test using a heart rate monitor. At the end of the test participants will complete a lap of slow walking as part of active recovery.

